**Table 3. Overview of Study Procedures and Measurements**

Study Procedures	Pre-Screening Phone Call	Study Visit #0 Screening	Study Visit #1 Baseline	Randomization Phone Call	Start Class #1 of 8-wk MBSR or SME	Study Visit #2 /Follow-up Phone Call	Study Visit #3	MBSR or SME Booster sessions	Study Visit #4 (End of study)
Timeline		Within 10 wks before Orientation	Within 6 wks before Orientation	Within 1 wk before Orientation	~1 wk after Orientation	Within 2 wks after Class #4	After Class #8 (2 months)	Once a month for 4 months	After Booster #4 (6 months)
Phone or In-person Intake Pre-Screen	x								
Written Informed Consent		x							
Class Schedule & Homework- Verify subject availability		x	x	x					
MINI structured interview		x							
Screening Assessments		x	x						
Phone Call Time Preference		x	x				x		
Orientation Questionnaire			x						
Stress Reduction Expectancy Scale (SRES)			x				x		x
Baseline Medical History			x						
Medications			x				x		x
Stress & Cravings Surveys			x	x	x	x	x	x	x
Daily Diary Surveys					x Start-up after Class #1	x	x	x	x
GLUCOSE CONTROL AND OTHER PHYSIOLOGIC OUTCOMES									
Primary Outcome: Hemoglobin A1ca		x Lab or Home Kit	x Lab & Home Kit				x Lab & Home Kit		x Lab & Home Kit
Fasting Glucose			x				x		x
Glucometer/CGM/insulin pump data		Date/Time check only	x				x		x
C-peptide (for HOMA-IR)			x				x		x
Fasting Lipids, hsCRP & TNF- $\alpha$			x				x		x
Saliva cortisol & $\alpha$ -amylase			x				x		x
Blood pressure & Heart rate			x				x		x
Weight, Height, and Waist and Hip Circumference			x				x		x
Body composition (Tanita scale measurements only – if in CRC)			x				x		x
Hair and nail samples (optional)			x				x		x
Urine pregnancy test	x	x					x		x
Hypoglycemia Survey		x			x	x			x
BEHAVIORAL OUTCOMES									
24-hour dietary recalls (optional)			x				x		x
Food Craving Questionnaire-Trait Reduced			x				x		x
Walking Enjoyment			x				x		x
Accelerometer data (optional)			x				x		x

Adherence to diabetes medications (Participant Questionnaire)			x				x		x
Counterfactual Measurement			x						x
PSYCHOSOCIAL OUTCOMES									
Toronto Mindfulness Scale (TMS)			x				x		x
Perceived Efficacy, Satisfaction, Engagement & Confidence							x		x
Diabetes Distress Scale			x				x		x
Perceived Stress Scale-10 (PSS-10)		x	x				x		x
Short Form-12 (SF-12)			x				x		x
Positive and Negative Affect (PANAS)			x				x		x
BRFSS (ACE survey)			x						
Childhood Trauma (CTQ)			x						
Modified Coronavirus Impact Scale			x				x		x
GAD-7			x				x		x
PROMIS Sleep Disturbance 8a			x				x		x
Safety screens (PHQ-9, and if indicated modified P4 Screener)		x	x				x		x
Stress Experience Survey			x			x	x		x

a Screening hemoglobin A1c: If the patient has a lab hemoglobin A1c result within 12 weeks and 2 days (86 days) before the start of the study intervention (Orientation), these records may be obtained, and after verifying the lab hemoglobin A1c result in the outside records or the EMR, the lab hemoglobin A1c result can be accepted in lieu of repeating the test for screening. If the patient does not have a lab hemoglobin A1c result within 12 weeks and 2 days (86 days) before the start of the study intervention, the screening hemoglobin A1c result will be obtained from either the Hershey Clinical Lab (if the screening visit is conducted in person), or from a Home A1cNow Self Check Kit (if the screening visit is conducted remotely).

In-person baseline, 2-month, and 6-month study visit hemoglobin A1c: When the baseline, 2-month, and 6-month study visits are conducted in person, hemoglobin A1c results will be obtained from both the Hershey Clinical Lab and from the Home A1cNow Self Check Kit. A lab hemoglobin A1c result obtained from the Hershey Clinical Lab within 2 weeks before the visit can be accepted as the study visit lab hemoglobin A1c. A screening Home A1cNow Self Check Kit hemoglobin A1c result within 2 weeks before the baseline visit can be accepted as the baseline home hemoglobin A1c.

Remote baseline, 2-month, and 6-month study visit hemoglobin A1c: When the baseline, 2-month, and 6-month study visits are conducted remotely, home hemoglobin A1c will be collected using the Home A1cNow Self Check Kit. A screening Home A1cNow Self Check Kit hemoglobin A1c result within 2 weeks before the baseline visit can be accepted as the baseline home hemoglobin A1c. If the subject has a lab result (e.g. lab hemoglobin A1c) outside of the study, the lab result (e.g. lab hemoglobin A1c) will be recorded as the study visit lab result (e.g. lab hemoglobin A1c) after verifying the result in outside records or the EMR.

Missed 2-month and 6-month (in-person or remote) study visits: If the subject misses their 2-month or 6-month study visit, and has a lab result (e.g. lab hemoglobin A1c) outside of the study, the lab result (e.g. lab hemoglobin A1c) will be recorded as the study visit lab result (e.g. lab hemoglobin A1c) after verifying the result in outside records or the EMR.

All subjects will be given the same general written guidelines on diet and exercise at the baseline visit, which will consist of two handouts downloaded from the American Diabetes Association Patient Education Library: (1) “Plan Your Portions” Diabetes Placemat and (2) “The Diabetes Advisor - Physical Activity.” All subjects will also be given handouts on Hyperglycemia and Hypoglycemia, as well as Glucometer Best Practices and Blood Glucose Meter Correlation, at the baseline visit. This will be the only information that will be the same across both groups. The MBSR group will not receive any additional health education other than these handouts.

**Baseline Laboratory Exam:**

Subjects will present to the baseline study visit in the CRC after a 10-hour fast (no food or drink, except for water) for collection of a single sample of blood. Additionally, subjects will be instructed not to eat or drink (except for water), chew gum, smoke, brush their teeth, exercise physically, or consume prescription or over-the-counter medications 60 minutes prior to presenting for their baseline study visit (as well as during the last 60 minutes of their baseline visit) to allow for collection of saliva samples.

In the fasting state, the research coordinator and/or CRC staff will collect a single blood sample of approximately 60 mL from each subject in order to measure hemoglobin A1c, glucose, c-peptide, lipid panel, high sensitive C-reactive protein (hsCRP), and TNF- $\alpha$ . The fasting glucose and c-peptide will be used to calculate the Homeostatic index of insulin resistance (HOMA-IR).

The blood draw for hemoglobin A1c will be in a lavender top tube (whole blood sample). The hemoglobin A1c assay must be run immediately by the Hershey Clinical Lab, however subjects will not be excluded based on their baseline lab hemoglobin A1c. A lab hemoglobin A1c result obtained from the Hershey Clinical Lab within 2 weeks before the baseline visit can be accepted as the baseline lab hemoglobin A1c, otherwise a lab hemoglobin A1c from the Hershey Clinical Lab will be obtained at in-person baseline study visits.

The samples for glucose, lipid panel and hsCRP will also be run immediately. Blood samples for c-peptide and TNF- $\alpha$  will be frozen at -80°C. The c-peptide samples will be collected in a green top with heparinized plasma and stored to be analyzed later under this protocol. The TNF- $\alpha$  samples will be stored to be analyzed later, but they will not be analyzed under this protocol. Validated assays with intra- and inter-assay coefficients of variation less than 15% will be used.

Within 5 minutes of having their blood drawn, subjects will be asked to check their glucose level via finger stick on their glucometer (optional), and via their continuous glucose monitor (if they have one). Research staff will compare glucose readings from the different sources to assess accuracy and calibration of subjects' devices. The research staff will notify subjects of discrepancies once lab reference glucose results are obtained, and advise subjects to refer to the Glucometer Best Practices and Blood Glucose Meter Correlation handout they were given at their baseline visit. Accuracy of glucometer will be defined as within 15% of lab reference value if  $\geq 100$  mg/dL, or within 15 mg/dL of lab reference value if  $< 100$  mg/dL (Klonoff et al., 2018). This is recommended when reporting glucose data in clinical research (Schnell et al., 2015). Glucometer brand and sub brand, test strip brand, and other important information regarding how subjects are using their diabetes devices will also be collected.

All of these laboratory assessments will be obtained at the baseline visit, 2-month visit and 6-month visit. If a study visit is conducted remotely, or if a subject misses a study visit, the research coordinator will obtain and record any available outside lab results, including hemoglobin A1c, glucose, and Lipid panel.

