**Table 1. Randomized trials of mindfulness-based group interventions in adults with diabetes.**

Author, year	Participants	Intervention	Duration of Intervention	Comparator	Is HbA1c a Primary Outcome?	Report intervention fidelity & quality and instructor characteristics?
Gregg, 2007	81 adults with type 2 diabetes	Acceptance and commitment therapy (ACT)	One day workshop of ACT plus diabetes education	Diabetes education only	YES	NO
Kopf, 2014	110 adults with type 2 diabetes and albuminuria	MBSR	8 weeks plus one booster session at 6 months	Treatment as usual	NO	NO
Miller, 2014	52 adults with type 2 diabetes	Mindful Eating Intervention	3 months	Diabetes education	YES	NO
Van Son, 2014	139 adults with type 1 or type 2 diabetes and low emotional well-being	Mindfulness-Based Cognitive Therapy	8 weeks	Waitlist control	NO	NO
Proposed Study	290 adults with uncontrolled type 1 or type 2 diabetes	MBSR extended with monthly boosters	6 months including 8-week MBSR	Stress Management Education (active control)	YES	YES

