### 2.3 Study Rationale

The proposed project uses mindfulness-based stress reduction (MBSR), a well-researched mindfulness-based intervention, to address stress as a critical barrier to glucose control in patients with diabetes. Stress is increasingly being recognized as an important factor contributing to poor glucose control and complications in individuals with diabetes (Hackett & Steptoe, 2017; Crump et al., 2016; Curry, 2016; Downs & Faulkner, 2015; Kelly & Ismail, 2015; Steptoe, 2016; Siddiqui et al., 2015; Fisher et al., 2010; Aikens, 2012; Hessler et al., 2014). **Figure 1** demonstrates a comprehensive model of the biological pathways by which stress potentially contributes to poor glucose control in diabetes. This project will assess the effects of MBSR on a meaningful subset of these constructs in adults with uncontrolled type 1 or type 2 diabetes. Although the etiological mechanisms underlying type 1 and type 2 diabetes are different, and individuals with type 2 diabetes have greater pancreatic beta cell reserve, the clinical manifestations and stressors of type 1 and type 2 diabetes are similar. Therefore, both adults with type 1 diabetes and adults with type 2 diabetes are likely to benefit from MBSR.

Mindfulness is among the top 50 priority topics for comparative effectiveness research recommended by the Institute of Medicine (2009). A comparative effectiveness review concluded that "Meditation programs, in particular, mindfulness programs, reduce multiple negative dimensions of psychological stress." (Goyal et al., 2014). Mindfulness-based stress reduction has been shown to reduce stress in various patient populations (Raja-Khan et al., 2017; Ludwig & Kabat-Zinn, 2008; Merkes, 2010; Nyklicek & Kuijpers, 2008; Burnett-Ziegler et al., 2016). In support of the biological pathways outlined in **Figure 1**, several systematic reviews and meta-analyses suggest that mindfulness based interventions such as MBSR have psychological, behavioral and physiological benefits in patients with chronic diseases (Levine et al., 2017; Rogers et al., 2017; Ruffault et al., 2017; Carriere et al., 2018; O'Reilly et al., 2014).

Dispositional mindfulness, an inherent but modifiable trait of the capacity to attend and to be aware of

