what is occurring in the present moment, has been inversely linked with obesity, a highly prevalent precursor to type 2 diabetes (Loucks et al., 2016). Mindfulness may be a novel determinant for glucose control in individuals with diabetes as it increases self-regulation and the ability to notice but not act on cravings (Epstein, 1999; Sedlmeier et al., 2012; Brewer et al., 2011; Loucks et al., 2015). Thus, one way MBSR could be helpful in the self-management of diabetes is by limiting the overconsumption of palatable high carbohydrate foods that increase blood glucose. Furthermore, as MBSR decreases stress and positively affects other key psychological factors often overlooked in standard approaches to diabetes, MBSR could significantly impact the clinical picture of diabetes by empowering patients with diabetes to adopt healthier behaviors (diet, exercise, self-monitoring of blood glucose, medication adherence) that improve their glucose control and reduce their risk of diabetes complications. MBSR could have beneficial physiologic effects on the hypothalamic-pituitary-adrenal (HPA) axis, sympathetic nervous system, and chronic inflammation, leading to reduced insulin resistance and improved blood glucose (Davidson et al., 2003; Carlson & Garland, 2005; Carlson et al., 2007; Winbush et al., 2007). MBSR could also exert beneficial effects by altering gene expression (Black & Slavich, 2016; Creswell et al., 2012; Dusek et al., 2008), as well as brain structure and function (Gotink et al., 2016; Mascaro et al., 2015; Muehsam et al., 2017; Santarnecchi et al., 2014). Several of these potential underlying mechanisms may act synergistically to mediate the impact of MBSR in diabetes.

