Randomization to MBSR or SME control will be performed within REDCap using a pseudo-random number generator via the PLAN procedure within SAS software, version 9.4 (SAS Institute Inc., Cary, NC). Personnel in the Department of Public Health Sciences will use the PLAN procedure within SAS software to generate a randomization list using variable-size, random permuted blocks to ensure that the number of subjects in each treatment arm is balanced after each set of B randomized subjects, where B is the block size. Using a 1:1 allocation ratio, there will be 145 subjects assigned to each study group. Randomization will be stratified by insulin vs. non-insulin treated subjects to make sure the two groups are balanced as this is a potential confounder. Personnel in the Department of Public Health Sciences will choose the block sizes without revealing it to any of the blinded investigators or study personnel who will be collecting and reviewing outcomes data. Study group data will be presented in a blinded fashion within DSMB reports.

Randomization to MBSR or SME control will be performed by the SME instructors in REDCap during the Randomization phone call as described below. Study group assignments will not be communicated to research personnel who will be collecting and reviewing outcomes data. The SME instructors will communicate the study group assignments to the subjects and the MBSR instructors. The subjects and instructors will be asked to keep the assignments concealed from the blinded investigators and study personnel. The PI, research coordinators and all study personnel involved in the collection and review of outcomes data will be blinded.

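### HOMA-IR is calculated with no limit by diabetes type, although in type 1 subjects the index carries no information on insulin resistance

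*Combined protocol and SAP*

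**What the plan says.** Under Baseline Laboratory Exam in section 7.2.3, study staff "will collect a single blood sample of approximately 60 mL from each subject in order to measure hemoglobin A1c, glucose, c-peptide" and further analytes, and "The fasting glucose and c-peptide will be used to calculate the Homeostatic index of insulin resistance (HOMA-IR". The same section adds that "All of these laboratory assessments will be obtained at the baseline visit, 2-month visit and 6-month visit". Table 3 carries the row "C-peptide (for HOMA-IR" under its heading for glucose control and other physiologic outcomes. No equation is given. Nothing limits the index by diabetes type or insulin use, or says how a very low C-peptide is handled.

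Table 1 describes the population as "290 adults with uncontrolled type 1 or type 2 diabetes", and section 3.1 sets no condition on type. Section 2.3 itself notes that "individuals with type 2 diabetes have greater pancreatic beta cell reserve". It also proposes a pathway through the stress axes and inflammation "leading to reduced insulin resistance and improved blood glucose". On insulin use, section 7.2.4 says: "Randomization will be stratified by insulin vs. non-insulin treated subjects".

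Section 8.3 sends physiologic data to a linear mixed model with insulin stratum as a fixed factor. Log transformation is allowed if the fit requires it. Type of diabetes is among the covariates that may be added. The mediation part of 8.3 names stress and leaves the list of other mediators open.

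**The concern.** HOMA-IR infers resistance from how much insulin the subject's own pancreas secretes at a given fasting glucose. Where there is little secretion to read, a low C-peptide reflects lost beta cells and not good sensitivity. Computing the index in type 1 subjects therefore produces a number that looks like low insulin resistance and moves only with glucose.

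What is at stake is a mechanistic claim. Aim 2 concerns physiological mechanisms, and insulin resistance is one of the pathways that the rationale proposes. TNF-α, saliva, hair and nail samples are stored but not analysed under this protocol, so HOMA-IR is one of the few laboratory mechanism measures that will be available. A pooled result could either hide a real effect in type 2 subjects or present a glucose effect in type 1 subjects as a change in resistance.

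**Working it through.** **The plan's own figure.** The documents give no design figure for HOMA-IR. The only one is the sample size for HbA1c in section 8.2: difference 0.5, SD 0.9, two-sided 0.05, 80% power, average group size 18, ICC 0.08, 15% dropout. A t-based calculation needs 52 per arm. The design effect is 1 + (18 − 1) × 0.08 = 2.36, so 52 × 2.36 = 122.7, rounded up to 123. Then 123 / 0.85 = 144.7, rounded up to 145 per arm, or 290 in total. The figure reproduces, and HOMA-IR does not enter it.

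**Assumed inputs for the index.** As no equation is stated, take the index as I = k × G × C, with G fasting glucose and C C-peptide. Assume G falls from 200 to 150 mg/dL. Assume C is constant at 0.02 nmol/L in a type 1 subject and at 1.0 nmol/L in a type 2 subject. None of these values is in the documents.

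**Level.** At equal glucose the type 1 index is 0.02 / 1.0 = 1/50 of the type 2 index. The result depends on the assumed C-peptide: at one half of the reference the ratio is 0.50, and at one tenth it is 0.10.

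**Change with C constant.** 150 / 200 = 0.75, a 25% fall. C cancels, so the relative change in the index is exactly the relative change in glucose.

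**Effect of the analysis scale.**
- Untransformed: type 1 changes by 0.02 × (150 − 200) = −1.0 k, and type 2 by 1.0 × (150 − 200) = −50 k. The type 1 change is 50 times smaller, close to nothing.
- Log: both change by ln(0.75) = −0.288, so the type 1 subject counts in full.

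**Effect on the group contrast.** Let s be the share of analysed subjects with type 1 diabetes. On the untransformed scale they add roughly zero, so the pooled difference is about (1 − s) times the type 2 difference: 0.9 of it at s = 0.1, 0.5 at s = 0.5. On the log scale, suppose the 25% glucose fall were an arm difference in type 1 subjects alone. The pooled contrast would then be s × (−0.288): −0.029 at s = 0.1, −0.086 at s = 0.3, −0.144 at s = 0.5. All of it would be glucose.

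**Whether the planned model repairs this.** A main effect for insulin stratum or diabetes type shifts the level of the index. It leaves the intervention-by-time contrast pooled over valid and invalid values.

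**Mediation.** With C constant, the index is fasting glucose times a constant. Using it to explain HbA1c explains one glucose measure by another.

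**Subjects left after a restriction to type 2.** 290 × 0.85 × (1 − s), halved in the last column:

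| Assumed type 1 share s | All 6-month visits in person | Half of them remote |
|---|---|---|
| 0.1 | 222 | 111 |
| 0.2 | 197 | 99 |
| 0.3 | 173 | 86 |
| 0.5 | 123 | 62 |

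The last column matters because no C-peptide is planned at remote visits.

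**The case against.** The best reply is that HOMA-IR hardly figures in the plan. It appears in one calculation sentence and one row label. Section 1.3 covers it at most by a general phrase, and the mediation text names stress. The pathway in section 2.3 is background, and the pilot saw no change in insulin resistance that would explain its fall in glucose. On the scale that 8.3 uses by default, type 1 subjects dilute the contrast and do not create a false benefit.

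Most of this stands, and it keeps the point small. It does not remove it: physiologic data do go to the model at 0.05 without multiplicity correction, a log transformation is foreseen, and other mediators are to be assessed in the same way as stress.

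A reader might go further and call the index invalid in every insulin-treated subject. The documents do not support that. The plan uses C-peptide, which does not count injected insulin, and the protocol offers no validity data for insulin-treated type 2 diabetes either way. Injected insulin can lower both glucose and C-peptide, so a dose change may move the index. That is confounding by treatment, and medication changes are recorded and will be explored under 8.3. It justifies showing the result by stratum, not discarding these subjects.

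**Conclusion.** The point holds for type 1 subjects. The plan, followed as written, gives them an index that carries no information on insulin resistance, and neither the stratum factor nor an optional covariate repairs it. The direction of the harm depends on the analysis: dilution on the untransformed scale, and a glucose change labelled as resistance on a log or ratio scale or in a mediation model. This rests on C-peptide being near its floor in type 1 subjects and on an index that rises with the product of glucose and C-peptide. Subjects with more residual secretion would be affected less.

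A reader might infer that the index will be wrong in much of the trial. That cannot be shown: neither the type 1 share nor the insulin-treated share is given, and subjects seen remotely will often have no index at all. Nor is HOMA-IR a named endpoint or mediator. HbA1c and the sample size of 290 are untouched. This is a cheap improvement to one secondary measure.

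**What to change.** In section 7.2.3, Table 3 and section 8.3:

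- Analyse HOMA-IR only in subjects with type 2 diabetes at baseline, and name the equation. Report fasting C-peptide descriptively in type 1. Diabetes type is already recorded at baseline, before randomization, so the restricted comparison stays randomized.
- Present the result by the insulin-treatment randomization stratum, with non-insulin-treated type 2 subjects as the main or a sensitivity analysis. Choose which in advance.
- Do not drop values because insulin was started after randomization. That would select on an event that may depend on glucose control and so on the intervention. Handle it in a sensitivity analysis.
- Do not use HOMA-IR as a mediator in any analysis that includes type 1 subjects.

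The cost is a few sentences and fewer subjects on this one index. No sampling changes, and because C-peptide is frozen for later assay, the rule can be set before results exist.
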